7.2. Sample Size Considerations

Based on information from a variety of studies a highly pessimistic assumption is that there would be a mean improvement of 0.5 with a standard deviation of 1.5. (These values refer to the 4-point scale.) Based on these assumptions, a sample size of 97 participants would result in a 90% power to detect an improvement using the paired-sample t-test. If data from multiple incidents per participant are useful, the power to detect an improvement would increase. The final sample size of 200 participants has been chosen to allow for various contingencies, including uncertainties about compliance in this self-reported trial, and the fact that some participants may not experience heartburn or indigestion during the trial period.

It should be emphasized that these assumptions are for sample size purposes only. Trial analysis will use the data as collected.

As discussed above, the number 200 may be increased based on observed data concerning the number of participants with indigestion and heartburn. The actual outcomes of treated participants will not be considered in this analysis, merely whether or not enrolled participants have reported starting using the test product. The method of reevaluating the sample size will be described in the Statistical Analysis Plan.

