2.2. Scientific Rationale

The test product's formulation is based on the most promising clinical research on natural ingredients that safely impact digestive health and relieve symptoms of occasional indigestion and heartburn. While the evidence to support the use of these individual active ingredients is growing, well-designed human clinical trials showing benefit are necessary to demonstrate efficacy of the test product's unique formulation.

The present study will include a minimum of 200 participants who suffer from the symptoms of mild to moderate indigestion and/or heartburn and is designed to observe the level of symptom reduction in this population after consuming the test product.

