5.1. Selection of the Study Population

The study population will consist of at least 200 participants who suffer from symptoms of indigestion and heartburn. The participants will otherwise be in good health.

The target sample size for this study is initially 200 participants, with a desired sample of 97 treated participants. This is described in detail in the Statistical Considerations section.

At such time as 180 participants have been enrolled, the available data will be analyzed using a constant hazard model to determine if it seems realistic that the desired number of 97 treated participants will be met by the end of follow-up. If the expected number of treated participants is less than 97, the target sample size will be increased as needed, considering both the desire for 97treated participants and the timelines of the trial sponsor. The actual outcomes of treated

participants will not be considered in this analysis, merely whether or not enrolled participants have reported starting using the test product.

Enrollment will be stopped once the target number of participants has been enrolled, no further participants will be offered a place in the trial once the target sample size criteria has been met. All participants who have already been offered places, but who have not yet consented, will be allowed to participate as long as they have signed the study consent within 15 days and the total number of participants does not exceed 125% of the target (either 200 or the recomputed target if recomputation has been performed.)

In order to ensure an age and sex distribution that is reasonably representative of the US population, enrollment may be stopped early in some age and sex groups.

Target population for this study are candidates who suffer from symptoms of occasional indigestion and heartburn.

Participants will be enrolled from across the United States. No participants will be enrolled outside of the United States. It is expected that the geographical distribution of the participants enrolled in the study will correlate with the geographical distribution of the general population across the United States.

Participants will be recruited via digital advertisements and social media.

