6.1. Study Procedures

- Candidates will review information about the study and complete a screening form.
- During the screening process, the candidate will be asked questions regarding their symptoms and medical history to ensure that they meet the requirements to participate in this study.
 Potential participants will also be asked questions to ensure that they do not meet any of the exclusion criteria and meet all of the inclusion criteria.
- After successful screening (participant does not meet any exclusion criteria), participants will review and sign study informed consent form.
- Upon verification of signed informed consent, participant will be enrolled into the study.
- At time of enrollment, participant will be given access to the HIPAA compliant study portal.
 - The study portal provides access to study information, signed informed consent form, instructions for test product use, frequently asked questions, study surveys, symptom diary, and data collection tools.
- Participant shall complete baseline assessments upon access to the portal.
 - Baseline assessment will include questions regarding the participants' demographics, medications, detailed information regarding their indigestion/heartburn including treatment.
- To ensure that baseline assessments are completed before test product is used by the
 participant, study materials and study welcome package will be shipped to the participant once
 the clinical study manager/clinical ops coordinator confirms that the baseline assessment has
 been completed.
- The welcome package will include an information sheet that will outline instructions for their participation in the trial, the test product, and paper forms of the documents (paper form of

- study documents will be provided for real time data collection, in the event that the participant cannot log into the study portal to input data).
- Once the participant receives the test product, the participant will log into the study portal to acknowledge the receipt of the test product.
- Study start date will be the reported date of receipt of test product.
- Participant will be sent weekly email reminders that remind them of their participation in the study.
- At the onset of the indigestion and heartburn episode, the participant will start a Symptom Diary and complete a 4-point Likert scale for each of the symptoms they are experiencing.
 - Onset is defined as the point in time the participant takes the test product for relief of symptoms.

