7.1. Study Outcomes Measures

Analysis populations:

The *intent to treat* (ITT) population consists of all participants who are consented, report the onset of indigestion and heartburn, and have taken the study medication at least once. The primary analysis will be in the ITT population.

Primary Endpoint:

The primary endpoint has two components, reduction in indigestion severity and reduction in heartburn severity. Participants will be asked to rate each symptom (bloating, early fullness during a meal, pain or discomfort in the upper abdomen, burning in the upper abdomen, pain/burning in the center of your chest, nausea, vomiting, burping) on a 4-point Likert scale at 4 time points: prior to taking the test product, 15, 30, and 60 minutes after taking the test product. The improvement in symptoms from baseline will be evaluated on a pairwise basis separately for each component and each time point. P-values will be computed for the improvement.

There is no control group for the primary analysis.

Secondary Endpoints:

Secondary endpoints will be gathered on the subjective experience of these participants related to general health, personal experience with the test product. The secondary endpoints will be self-reported by the participant on their online portal. There will be a questionnaire related to general health and the subjective experience of the participant administered at baseline and at study exit.

The purpose of the secondary analyses is to investigate the association between various baseline and other measurements and outcomes. These secondary analyses are considered hypothesis generating, and the descriptions are somewhat informal. The trial data may suggest secondary analyses not described here.

Secondary endpoints:

- The time to other intervention will be analyzed.
- A longitudinal analysis will be performed for participants who report on more than one incident of heartburn or indigestion.
- Adverse events will be summarized.
- An additional data presentation will consist of results from both Treatment and Control
 in similar studies appearing in the literature. There will be no formal statistical
 comparison of results from this study and historical studies.
- The Net Promoter Score will be summarized and compared against outcomes.
- Comparison against normal behavior will use the paired sample t-test.

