7.3. Analysis Plan

Separate tables will be presented showing the changes from baseline for each component and each time point. The changes will be evaluated by the paired sample t-test. A longitudinal analysis will be performed for participants who report on more than one incident of heartburn or indigestion.

General statistical methods:

Data will be analyzed using standard statistical methods, as further specified in a statistical analysis plan (SAP), which will be prepared in detail later.

- Data analysis will largely consist of summary statistics and graphs. The only formal group comparisons will be in covariate analyses.
- For continuous variables data presentation will consist of means, confidence intervals computed using the *t*-statistic, medians, and interquartile ranges. Group comparisons will use *t*-tests or ANOVA.
- For discrete variables confidence intervals will use the exact intervals, where available. Group comparisons will use Fisher's exact test, with the Monte Carlo version used where computationally necessary.
- For time to event variables analysis will use the Kaplan-Meier algorithm, and group comparisons will use the log-rank or proportional hazards methods, depending on the data type.
- Visual analog scale values will be treated as continuous variables. Frequency counts will also be provided for scales with 10 or fewer distinct response levels.
- Covariate analyses will investigate the relation between baseline and outcome variables, using methods appropriate to the data types involved. Age, gender, and baseline medications will be included in these analyses where appropriate data are available.
- Present intention is that the analysis will be performed in R, and the precise form of algorithms will be the default of R. Kaplan-Meier, log-rank, and proportional hazards algorithms will be the defaults of the survival package.

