13.1.3. Appendix C Screening Form

Screening

Please answer the following questions to the best of your abilities.

- 1. Are you at least 18 years old? (DOB?)
- 2. Do you suffer from symptoms of indigestion and/or heartburn (see severity index below)? (Y/N)
- 3. Have you ever been diagnosed with any chronic liver disease? (Y/N)
- 4. Have you ever been diagnosed with any chronic renal disease? (Y/N)
- 5. Are you pregnant or breastfeeding? (Y/N)
- 6. Do you have any allergies to any of the following? (Y/N)
 - a. Licorice
 - b. Artichoke leaf
 - c. Marshmallow Root
 - d. Ginger
 - e. Chamomile
 - f. Rice Hull Concentrate
 - g. Carrageenan
 - h. Cellulose Capsule
- 7. Do you have more than 10 alcoholic beverages per week? (Y/N)
- 8. Are you willing to try the test product for relief of your indigestion and heartburn symptoms? $(\frac{Y}{N})$
- Have you been prescribed any medication by your doctor for any GI disorder or medication that can affect the GI system? (Y/N)
- 10. Have you ever had surgery of the upper GI tract or abdominal surgery (with the exception of having your gallbladder or appendix removed)? (Y/N)
- 11. Are you currently taking any anticoagulation, blood-thinning, medication daily (aspirin, warfarin, etc.)? (Y/N)
- 12. Are you able to swallow pills? (Y/N)

Severity index

Dyspepsia: Dyspepsia Symptom Severity Index (DSSI)

Aims

To develop a self-report measure to quantify the severity of dyspepsia symptoms in clinical practice and research.

Dyspepsia symptom severity index (DSSI) Scale/item Dysmotility-like 1. Frequent burping or belching 4. Bloating 5. Feeling full after meals 6. Inability to finish normal-sized meals 7. Abdominal (belly) discomfort, without pain, after meals 8. Abdominal (belly) distension (feels as though you need to loosen your clothes) 12. Nausea before meals 13. Nausea after meals 14. Nausea when you wake up in the morning 15. Retching (heaving as if to vomit, with little result) 16. Vomiting Reflux-like 3. Burping with bitter tasting fluid in throat 17. Regurgitation of bitter fluid into your mouth (reflux) during the 18. Regurgitation (reflux) at night 19. Burning feeling in your chest (heartburn) 20. Burning feeling in your stomach 9. Abdominal (belly) ache or pain right after meals 10. Abdominal (belly) pain before meals or when hungry 11. Abdominal (belly) pain at night Overall item

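### Does the 90% power at 97 treated participants fail for indigestion or heartburn because a participant may have only one of them?

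*Combined protocol and SAP*

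**What the plan says.** Section 7.2 gives one mean improvement (0.5), one SD (1.5) and one test, and concludes that "a sample size of 97 participants would result in a 90% power to detect an improvement using the paired-sample t-test". It calls these assumptions highly pessimistic, notes that several incidents per participant could add power, and sets enrolment at 200 to cover contingencies that include participants with no episode.

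Section 7.1 has two primary components, indigestion severity and heartburn severity, each compared with baseline at 15, 30 and 60 minutes. It states that "The primary analysis will be in the ITT population", meaning consented participants who report onset and take the product at least once. Section 7.3 adds: "Separate tables will be presented showing the changes from baseline for each component and each time point".

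Section 2.2 reads: "The present study will include a minimum of 200 participants who suffer from the symptoms of mild to moderate indigestion and/or heartburn". The screening form (Appendix C) asks: "Do you suffer from symptoms of indigestion and/or heartburn".

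The check at 180 enrolled (Section 5.1) works to a target of 97 treated participants: "If the expected number of treated participants is less than 97, the target sample size will be increased as needed". It considers no outcomes, "merely whether or not enrolled participants have reported starting using the test product".

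Section 6.1 has the participant "complete a 4-point Likert scale for each of the symptoms they are experiencing", whereas Section 7.1 has each listed symptom rated and the diary (Appendix E) offers 0, no symptom, for every item.

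**The concern.** A participant who enters with only one complaint may score 0 on the other component before dosing, and a score of 0 cannot improve. Section 7.2 does not say whether 0.5 and 1.5 describe everyone treated or only those who have the component. If the latter, 97 treated participants provide fewer than 97 who can improve on the less common component. The check at 180 would not reveal this, because it counts product use alone.

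Two details add to the doubt. The eight listed symptoms are not assigned to the two components. And the looser wording in Section 6.1 leaves room for an absent symptom to be either a zero change or a missing value.

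At stake would be the stated power for one component and the meaning of its mean change. A mean of 0.5 among those affected becomes 0.5 × 0.9 = 0.45, 0.5 × 0.75 = 0.375 or 0.5 × 0.5 = 0.25 over all treated. Section 7.3 sets these results beside historical studies, some of which report only one of the two conditions.

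**Working it through.** **Inputs.** Mean 0.5, SD 1.5, n = 97 and power 90% come from Section 7.2. Alpha is not stated; two-sided 0.05 is assumed because it reproduces 97. The share *p* of treated participants who have a given component at onset is not in the documents; 90%, 75% and 50% are assumed to show a range.

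**Step 1: the plan's figure.** Paired t-test power comes from the noncentral t distribution with n − 1 degrees of freedom and noncentrality (0.5/1.5)√n. For n = 97 the noncentrality is 0.3333 × 9.849 = 3.283 and power is 0.9015. For n = 96 power is 0.8985. So 97 is the smallest n that gives 90% for one test.

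**Step 2: 0.5 and 1.5 as averages over all treated.** Power is 0.9015 for each component, with no loss. The implied mean among those who have the component is 0.5/p: 0.56, 0.67 or 1.00.

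**Step 3: 0.5 and 1.5 as values among those who have the component.** In the planned all-treated test the others contribute a change of zero, so the mean is 0.5p and the variance is p(1.5² + 0.5²) − (0.5p)².

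| p | Mean | SD | Power, 97 treated | Power, 200 treated |
|---|---|---|---|---|
| 0.90 | 0.45 | 1.43 | 0.866 | 0.993 |
| 0.75 | 0.375 | 1.32 | 0.793 | 0.980 |
| 0.50 | 0.25 | 1.09 | 0.609 | 0.898 |

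If absent components were left unrated instead, 87, 72 or 48 of the 97 would be analysed, with power 0.867, 0.797 or 0.619. The handling of absent symptoms therefore barely affects power. In the all-treated test, 0.80 is reached when 74 of 97 have the component (0.800); 73 gives 0.794.

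**Step 4: dependence on the pessimistic values.** If nobody worsens, a change on a 0–3 item lies between 0 and 3. The largest SD for a mean of 0.5 is then √(0.5 × 2.5) = 1.118. With that SD among those affected, the all-treated test at 97 has power 0.984, 0.958 or 0.836, and 90% is kept while 58 of 97 (60%) have the component. With SD 1.5 but a mean of 0.75 among those affected, power is 0.995, 0.984 or 0.901.

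**The case for a change.** The strongest case for acting is that the ambiguity is certain even if the power loss is not. Naming the ITT population fixes who is tested, not whom 0.5 and 1.5 describe. Because the check reacts only when fewer than 97 treated are expected, the plan accepts an ending at 97, so the margin in 200 is not guaranteed. The SAP is still to be written, so clarification would be cheap. A count at 180 of treated participants with a pre-dose score of at least 1 on each component would use no post-dose outcome, and a supportive table in those participants would separate how common a component is from how far it is relieved.

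Part of this stands. The symptoms are not assigned to components, Section 6.1 is looser than Section 7.1 and the diary, and the set behind 0.5 and 1.5 is not spelled out. But Section 5.1 expresses the target as treated participants and Section 7.1 analyses that same set, so the plain reading is that the assumptions refer to it. The diary prints a zero option for every symptom, which settles in practice how an absent one is recorded. The inclusion criterion in Section 5.2 names indigestion, so a low share is mainly a heartburn question.

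The proposed additions gain little. The extra count would carry no decision rule, and nothing in the plan depends on reaching 90%. A table restricted to participants who start at 1 or more is more exposed to regression to the mean, which matters in a study without a control group, and it omits symptoms that first appear after dosing. Section 7.3 already promises frequency counts for short scales, so pre-dose zeros can be shown beside the means.

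**Conclusion.** No change is needed. The 97 and 90% are right for one paired t-test, on the assumed two-sided 0.05, and they are not shown to be wrong for either component. Power falls to 0.87, 0.79 or 0.61 only if several things hold together: 0.5 and 1.5 describe a subset the plan never defines, 90%, 75% or 50% of those treated belong to it (an assumption; the documents give no figure), the pessimistic effect and SD both apply, and treated numbers end near 97. At the smaller SD of 1.118 the same shares give 0.98, 0.96 and 0.84.

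The remaining points, namely which symptoms make up each component, which set the planning values describe, and the wording in Section 6.1, are missing detail that analysts can settle sensibly from the diary and Section 7.1 when the SAP is written. They leave the primary analysis, its validity and the enrolment rule as they are.

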7.3. Analysis Plan

Separate tables will be presented showing the changes from baseline for each component and each time point. The changes will be evaluated by the paired sample t-test. A longitudinal analysis will be performed for participants who report on more than one incident of heartburn or indigestion.

General statistical methods:

Data will be analyzed using standard statistical methods, as further specified in a statistical analysis plan (SAP), which will be prepared in detail later.

- Data analysis will largely consist of summary statistics and graphs. The only formal group comparisons will be in covariate analyses.
- For continuous variables data presentation will consist of means, confidence intervals computed using the *t*-statistic, medians, and interquartile ranges. Group comparisons will use *t*-tests or ANOVA.
- For discrete variables confidence intervals will use the exact intervals, where available. Group comparisons will use Fisher's exact test, with the Monte Carlo version used where computationally necessary.
- For time to event variables analysis will use the Kaplan-Meier algorithm, and group comparisons will use the log-rank or proportional hazards methods, depending on the data type.
- Visual analog scale values will be treated as continuous variables. Frequency counts will also be provided for scales with 10 or fewer distinct response levels.
- Covariate analyses will investigate the relation between baseline and outcome variables, using methods appropriate to the data types involved. Age, gender, and baseline medications will be included in these analyses where appropriate data are available.
- Present intention is that the analysis will be performed in R, and the precise form of algorithms will be the default of R. Kaplan-Meier, log-rank, and proportional hazards algorithms will be the defaults of the survival package.
- The exact items to be compared depend on what is reported in each historical control study. When possible, the items will include symptom relief at each time measured, including within-participant p-values, and time to the lowest level on a 4-point scale and to the lowest 2 levels on a 10-point scale. as well as reported baseline characteristics. When two-arm studies are compared, both arms will be reported in this comparison. In some studies, only indigestion or heartburn will be reported; when both are reported they will be separated for the comparison. Specific studies to be considered will be identified prior to the analysis of actual trial data.

8. Informed Consent Process

The study protocol and informed consent will be reviewed and approved by Advarra Institutional Review Board prior to study start.

Study candidates will learn about the study via digital advertisements. If interested in learning more, they will be referred to a website "landing page" that will provide detailed information about the study. They may opt to complete a screening survey ascertaining study eligibility through patient reported outcomes. If successfully completed (no exclusion criteria are selected), candidate will be invited to review the study consent form tutorial which includes the opportunity to ask questions related to the study from the Principal Investigator or delegated authority of the investigator. Candidate will be provided with contact information to reach investigator or study manager as desired.

Candidate may sign the informed consent via electronic signature as provided by Hawthorne Effect. The study manager will verify candidate signature prior to enrollment as a study participant.

9. Subject Confidentiality

All participants' data and personal information will be kept confidential. Only those involved with the study will have access to participant information. The data will be stored by Hawthorne Effect on a HIPAA compliant platform. The platform, which the data is stored on, will require a personalized username and password to gain access.

10. Publication

This study will be registered on clinicaltrials.gov prior to commencement of enrollment the results will be analyzed and submitted for publication.

11. Limitations

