- After completing the surveys, the participant will take the test product. The participant will take
 2 capsules per indigestion and heartburn episode. With a max of 6 capsules per day. (If
 participant takes 6 capsules in 1 day this will be defined as 3 indigestion and heartburn episodes
 and the participant will be exited from the study).
- After taking the test product, the participant will complete a 4-point Likert scale assessment for each symptom at 15 minutes, 30 minutes, and 1 hour after taking the test product.
- When the participants symptoms have resolved , the participant will complete the symptom diary.
- If the participant takes any other medication outside of the test product, the participant will record this on the symptom diary.
 - The participant is allowed to take alternative medications or supplements AFTER 1 hour from taking the test product.
- After taking the test product, the participant will be instructed to fill out an Adverse Event form for any side-effects experienced.
- After the first episode of indigestion and heartburn, the participant will be asked to complete the same process for another 2 episodes within the 60-day study time frame; however, these are not required.
- If the participant completes the required assessments for a total of 3 episodes of indigestion and heartburn, they will be prompted, by email, to exit the study.
- If the participant only completes the required assessments for the required 1 episode of indigestion and heartburn, the participant will be prompted, by email, to complete the study exit form and will be exited from the study on day 60 (60 days from the day of receipt of the test product).
- Neither the sponsor nor Hawthorne Effect Inc. will not collect any unused test product.
- Upon receipt of study exit survey and review of completed study forms, participant will receive an Amazon gift card of \$25 via email.

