Dain or Discomfort in the	Unner Abdemen				
Pain or Discomfort in the	Opper Abdomen	2	3		
No Symptom	Slight	Moderate	Severe		
Burning in the Upper Ab	domen				
0 No Symptom	1 Slight	2 Moderate	3 Severe		
Pain/Burning in the center	er of your chest				
0	1	2	3		
No Symptom	Slight	Moderate	Severe		
Nausea					
0	1	2	3		
No Symptom	Slight	Moderate	Severe		
Vomiting					
0	1	2	3		
No Symptom	Slight	Moderate	Severe		
Burping					
0	1	2	3		
No Symptom	Slight	Moderate	Severe		
Other:	1	2	3		
0 No Symptom	Slight	Moderate			
No Symptom	Stight	Woderate	Severe		
60 Minutes afte	er taking the	e test product			
Bloating					
0	1	2	3		
No Symptom	Slight	Moderate	Severe		

Early Fullness During a Meal 0 No Symptom	1 Slight	2 Moderate	3 Severe		
Pain or Discomfort in the Upp 0 No Symptom	oer Abdomen 1 Slight	2 Moderate	3 Severe		
Burning in the Upper Abdom 0 No Symptom	en 1 Slight	2 Moderate	3 Severe		
Pain/Burning in the center of 0 No Symptom	your chest 1 Slight	2 Moderate	3 Severe		
Nausea 0 No Symptom	1 Slight	2 Moderate	3 Severe		
Vomiting 0 No Symptom	1 Slight	2 Moderate	3 Severe		
Burping 0 No Symptom	1 Slight	2 Moderate	3 Severe		
Other: 0 No Symptom	1 Slight	2 Moderate	3 Severe		
After your symptoms resolveplease complete any of the following questions if applicable.					
Did your symptoms resolve completely with the test product? Yes No Time of complete symptom resolution:					

Did you need to take another medication	on: Yes N	No
Medication #1:	Dose:	Time:
Medication #2:	Dose:	Time:
Medication #3:	Dose:	Time:
Did your symptoms resolve completely	with taking your altern	native medication? Yes No
After taking the alternative medication,	, time of complete resol	lution of symptoms:

Did you experience any side effects after taking the test product? (Y/N) If yes, **Please fill out** the Adverse Event form.

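### Section 7.3 names Kaplan-Meier but gives no rule for episodes that resolve without another remedy; if they are censored at resolution, use of another remedy is overstated

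*Combined protocol and SAP*

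**What the plan says.** Section 7.1 lists the endpoint in one line: "The time to other intervention will be analyzed". The method comes from the general list in section 7.3: "For time to event variables analysis will use the Kaplan-Meier algorithm". Group comparisons are by log-rank or proportional hazards, and "Kaplan-Meier, log-rank, and proportional hazards algorithms will be the defaults of the survival package". No time origin, horizon, censoring rule, choice of episode or competing-event method is given. Section 7.3 describes the methods "as further specified in a statistical analysis plan (SAP), which will be prepared in detail later".

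The conduct sections shape the data that this analysis would receive:

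- Section 6.1 sets the earliest permitted event: "The participant is allowed to take alternative medications or supplements AFTER 1 hour from taking the test product".
- Also in section 6.1, once symptoms are gone, "the participant will complete the symptom diary".
- The diary (Appendix E) has a field headed "Time of complete symptom resolution" and, separately, the time of each other medication.
- The baseline form (Appendix D) offers usual durations of 0-30 minutes and 31 minutes to 1 hour, so some episodes may end before any other remedy is permitted.

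On the status of the endpoint, section 7.1 says: "These secondary analyses are considered hypothesis generating, and the descriptions are somewhat informal".

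**The concern.** Kaplan-Meier treats a censored participant as someone who would go on to have the event at the same rate as those still under observation. That is reasonable for a participant who stops reporting. It is not reasonable for one whose episode is over.

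For an episode without rescue, resolution is the last time that the diary records, and no horizon directs the analyst elsewhere. Entering resolution as a censoring time is therefore the coding most likely to follow from these data. The curve would then describe rescue as if no episode ever resolved, while being read as the share of treated participants who needed something else.

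This matters because section 7.3 says the analysis will consist mostly of summaries and graphs, so the curve may well be the reported result. The synopsis says the data will describe the product's performance and may inform a later two-arm trial. An inflated rescue figure would misstate the first and could mislead the second.

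**Working it through.** The protocol gives no expected rate of rescue or resolution, so there is no figure for this endpoint to reproduce. The number 97 below is the desired number of treated participants in sections 5.1 and 7.2, used only as a convenient denominator. All rates and counts are assumptions.

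**1. Direction, with assumed counts.** Of 97 treated, 48 resolve at 40 minutes, 20 take another remedy at 90 minutes and 29 resolve at 120 minutes.

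- True share: 20/97 = 20.6%.
- Censored at resolution: 97 − 48 = 49 remain at risk at 90 minutes, so 1 − KM = 20/49 = 40.8%.
- Kept event-free in the risk set to 240 minutes: 1 − KM = 20/97 = 20.6%.

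The overstatement comes from removing resolved episodes as censored. Keeping them in the risk set to a common horizon gives the correct share.

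**2. Size among episodes unresolved at 60 minutes.** Let λ be the total hazard per hour after the 60-minute report, p the eventual share rescued, and t the hours since that report. Rescue has hazard pλ and resolution (1 − p)λ.

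- Censoring at resolution: 1 − KM(t) = 1 − exp(−pλt)
- True cumulative incidence: CIF(t) = p[1 − exp(−λt)]

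With λ = 1 and t = 3 (4 hours after dosing), 1 − exp(−3) = 0.950:

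| p | 1 − KM | CIF | Gap | Ratio |
|---|---|---|---|---|
| 0.15 | 1 − exp(−0.45) = 0.362 | 0.143 | 22 points | 2.5 |
| 0.25 | 1 − exp(−0.75) = 0.528 | 0.238 | 29 points | 2.2 |
| 0.40 | 1 − exp(−1.20) = 0.699 | 0.380 | 32 points | 1.8 |

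The result depends on λ. For p = 0.25 and t = 3, halving λ to 0.5 gives 1 − exp(−0.375) = 0.313 against 0.25 × [1 − exp(−1.5)] = 0.194. Doubling λ to 2 gives 1 − exp(−1.5) = 0.777 against 0.25 × [1 − exp(−6)] = 0.249.

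**3. Adding the first hour.** Let f be the share of treated participants who resolve within 60 minutes. If no one takes another remedy before then, those participants leave the risk set before the first event, so 1 − KM does not change. The true share among all treated becomes (1 − f) × CIF. For f = 0.5 and p = 0.40 it is 0.5 × 0.380 = 0.190, against 0.699.

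Simulation agrees (97 participants, 1,000 repeats per cell, λ = 1, 240 minutes after dosing). Each cell shows 1 − KM with censoring at resolution, against the true share of all treated:

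| Resolved in first hour | 20% of the rest rescued | 40% | 60% |
|---|---|---|---|
| 30% | 45.6% v 13.4% | 69.5% v 26.5% | 83.5% v 40.2% |
| 50% | 45.1% v 9.4% | 69.8% v 19.0% | 83.8% v 28.4% |
| 70% | 43.2% v 5.5% | 69.8% v 11.5% | 83.1% v 17.1% |

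Down each column the true share falls while the Kaplan-Meier figure hardly moves, because first-hour resolvers contribute nothing to it. In every cell, keeping resolved episodes event-free to 240 minutes reproduced the true share.

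**The case against.** The strongest reply is that the harmful coding is inferred. The Kaplan-Meier line is a general methods statement, details are left to a later SAP, and section 6.2 schedules the last diary entry of an episode at 60 minutes, although section 6.1 has the diary completed at resolution. An analyst could choose a fixed horizon and obtain the right answer. This stands as a limit on the claim. A reader might infer that the plan as written will overstate rescue, but the documents do not settle the coding and support only the conditional statement. It does not remove the point, because nothing in the protocol directs the analyst to a horizon.

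Second, the simple share is available without Kaplan-Meier. The diary has a yes/no item on needing another medication, the exit form asks a related question, and section 7.3 provides exact intervals for discrete variables. That is true and lowers the stakes. It also means that the report could carry two conflicting figures for the same quantity.

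Third, if resolution is censored, the log-rank and proportional hazards comparisons already in section 7.3 are cause-specific comparisons. That stands: they need a label, not replacement.

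Fourth, every rate in the calculation is assumed. That also stands. The direction under censoring at resolution does not depend on the rates, but the size does.

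**Conclusion.** The point holds conditionally. The protocol names plain Kaplan-Meier for an endpoint with a competing event and gives no rule for that event. If resolved episodes are censored at resolution, one minus Kaplan-Meier overstates the share who took another remedy. Among episodes unresolved at 60 minutes, with constant hazards totalling 1 per hour, the estimate three hours later is 1.8 to 2.5 times the true share for eventual rescue between 40% and 15%. Among all treated participants the ratio is larger if some resolve within the first hour.

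Three further readings go too far:

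- A reader might infer that leaving resolved episodes at risk causes the bias. The arithmetic shows the reverse.
- A reader might infer that the gap always widens as more participants resolve. Over the assumed range the ratio rises, but the gap in percentage points shrinks from 32 to 22.
- A reader might infer that this is the only time-to-event item. Section 7.3 also lists time to the lowest symptom level for the historical presentation.

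Severity is low. The endpoint is secondary and hypothesis generating, and the primary paired t-tests are untouched.

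**What to change.** In section 7.3 or the later SAP, define the endpoint on the first treated episode, with time zero at dosing and a stated horizon. The event is another remedy, and the competing event is complete resolution without one. Censoring is kept for episodes whose status is unknown, such as incomplete diaries. Report the Aalen-Johansen cumulative incidence, which the survival package already named in section 7.3 produces from a multi-state status. If status is known to the horizon for every episode, keeping resolved episodes event-free to that horizon gives the same figure. Log-rank and proportional hazards comparisons can stay if they are labelled cause-specific.

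The cost is a sentence or two. Both times are already on the diary, so no new data, visit or sample size change is needed.
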